5.3 Surgery

Protocol Version: 05/16/2023 Page 17 of 45

Once patients are deemed eligible for surgical resection, surgery should ideally be performed no later than 8 to 10 weeks after completing chemoradiation. In the post-operative period for patients who undergo surgery, postoperative complications will be scored by the surgeons and/or nursing/research staff at the post-op visit with the surgeon and will be recorded.

5.4 Patient-Reported Outcomes Measures (PROs)

Treatment-related symptom scores and QOL will be assessed by a research coordinator at the following time points:

- prior to the start of therapy
- at the end of chemoradiation (day of EOT or up to 1 week after)
- 2 months (+/- 2 weeks) following the end of chemoradiation; this should be just prior to surgery for those patients undergoing surgery who have received CRT but not definitive chemotherapy
- 4 months (+/- 2 weeks) following the end of chemoradiation; this should be just prior to surgery for those patients undergoing surgery who have received CRT + definitive chemotherapy and should be approximately 2 months following surgery for those patients undergoing surgery who have received CRT but not definitive chemotherapy
- 6 months (+/- 2 weeks) following the end of chemoradiation; this should be approximately 2 months following surgery for those patients undergoing surgery who have received CRT + definitive chemotherapy
- 9 months following the end of chemoradiation
- 12 months following the end of chemoradiation

The QOL and other PRO assessments will be conducted using a computer-assisted interview program, and may be done in person before/after a routine office visit or over the phone at the preference of the study participant.

Regardless of whether the patient had surgery, clinical outcomes and treatment-related toxicity will continue to be captured at each follow-up visit after Month 12 along with standard clinical assessments. Follow-up visits are typically are done at intervals of 3-4 months for the first 2 years after completion of last treatment procedure, and every 6 months for the 3 years thereafter.

5.5 Women of Childbearing Potential

Women of childbearing potential (defined as women with regular menses, women with amenorrhea, women with irregular cycles, women using a contraceptive method that precludes withdrawal bleeding, and women who have had a tubal ligation) are required to have a negative pregnancy test within 7 days prior to study entry.

Female and male patients (along with their female partners) are required to use two forms of acceptable contraception, including one barrier method, during participation in the study.

Protocol Version: 05/16/2023 Page 18 of 45

If a patient is suspected to be pregnant, study treatment should be immediately discontinued. In addition, a positive urine test must be confirmed by a serum pregnancy test. If it is confirmed that the patient is not pregnant, the patient may resume dosing.

If a female patient or female partner of a male patient becomes pregnant during therapy or within 3 months after the last study treatment, the investigator must be notified in order to facilitate outcome follow-up.

5.6 Duration of Therapy

If at any time the constraints of this protocol are considered to be detrimental to the patient's health and/or the patient no longer wishes to continue protocol therapy, the protocol therapy should be discontinued and the reason(s) for discontinuation documented in the case report forms.

In the absence of treatment delays due to adverse events, PBT may continue for 6 weeks and QOL assessments for one year after the end of CRT or until one of the following criteria applies:

- Documented and confirmed disease progression
- Death
- Adverse event(s) that, in the judgment of the investigator, may cause severe or permanent harm or which rule out continuation of study drug
- General or specific changes in the patient's condition render the patient unacceptable for further treatment in the judgment of the investigator
- Suspected pregnancy
- Serious noncompliance with the study protocol (if the patient is noncompliant with their recommended treatment, rendering his/her QOL data not usable)
- Lost to follow-up
- Patient withdraws consent
- Investigator removes the patient from study
- The Siteman Cancer Center decides to close the study

5.7 **Duration of Follow-up**

Follow-up visits are typically done at intervals of 3-4 months for the first 2 years after completion of last treatment procedure, and every 4-6 months thereafter for the next 3 years.

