2.0 OBJECTIVES

2.1 Primary Objectives

- 1. To assess patient-reported outcomes of proton beam therapy (PBT) for esophageal cancer at 6 months following chemoradiation.
- 2. To assess physician-reported toxicity of PBT for esophageal cancer.
- 3. To assess patient-reported outcomes of PBT for esophageal cancer at 12 months following chemoradiation.

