5.1 Chemotherapy

Since this is a radiation modality trial, all patients suitable for concurrent chemotherapy with or without experimental therapies on clinical trials or for induction chemotherapy prior to neoadjuvant concurrent chemoradiation and patients receiving definitive concurrent chemotherapy and radiation are eligible for this study. This study will not mandate use of any one regimen but will defer to the treating oncologist's recommendations.

Dose adjustments for all chemotherapy agents may be made per physician discretion/preference. It is not a protocol violation for changes in a chemotherapy regimen during treatment if that is the deemed necessary by the treating medical oncologist. All chemotherapies will be prepared and administered in accordance with the prescribing information approved by the Food and Drug Administration (FDA) or other regulatory agencies.

Typically, neoadjuvant chemotherapy is completed at the time of the completion of concurrent radiation therapy. Patients receiving definitive therapy typically receive an additional 4 to 8 weeks of chemotherapy after radiation therapy has been completed.

All chemotherapy labs and procedures will be collected and performed following the standard of care process and timeline.

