11.4 Patient Reported Outcomes

We will calculate descriptive statistics (mean, standard deviation, etc.) for all QOL data (EQ-5D, SF-12) in addition to other PROs (depressive symptoms, social support) at each evaluation period. Univariate tests will explore the associations among QOL and PROs using analysis of variance (ANOVA) and Fisher's exact test for correlation. Changes over time in QOL and PROs will be analyzed utilizing repeated-measures modeling techniques

Protocol Version: 05/16/2023 Page 26 of 45

(repeated measures analysis of covariance).

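### Section 5.6 ends QOL assessments and labels QOL data unusable after serious noncompliance, which, if applied, would make the primary patient-reported results conditional on adherence

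*Combined protocol and SAP*

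**What the plan says.** Section 2.1 makes patient-reported outcomes primary at two times. The first objective reads "To assess patient-reported outcomes of proton beam therapy (PBT) for esophageal cancer at 6 months following chemoradiation", and the third repeats it for 12 months. Neither is restricted to patients who complete or comply with treatment.

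Section 5.6 says how long proton therapy and QOL follow-up last. It provides for "QOL assessments for one year after the end of CRT or until one of the following criteria applies" and then lists the criteria. One of them is serious noncompliance with the protocol, which a parenthesis qualifies as "if the patient is noncompliant with their recommended treatment, rendering his/her QOL data not usable". No other item in the list comments on the usability of data.

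Section 11.4 states: "We will calculate descriptive statistics (mean, standard deviation, etc.) for all QOL data". It goes on to other patient-reported measures and a repeated-measures analysis of change. It defines no analysis population, does not repeat the exclusion and gives no method for missing data.

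Section 5.1 leaves the chemotherapy regimen to the treating oncologist and says "It is not a protocol violation for changes in a chemotherapy regimen during treatment" if that oncologist finds the change necessary.

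**The concern.** Compliance with treatment is observed after baseline and can depend on how the patient is feeling. A patient who misses fractions, refuses chemotherapy or declines a recommended step may do so because of pain, fatigue, nausea or difficulty swallowing, and these are items of the MDASI-Plus (Appendix B). Losing such patients from a primary summary changes the question from how patients fare on proton therapy to how adherent patients fare on it. In a single-arm trial there is no control group subject to the same loss.

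The clause can act in two ways. The list in 5.6 ends later QOL assessments, so answers at months 6 and 12 may never be collected. The label can also be read to cover answers already given, such as those at baseline, end of chemoradiation and months 2 and 4, which feed the repeated-measures model. The protocol does not say whether those are kept. Since 5.6 and 11.4 point in different directions, an analyst could keep or drop these patients after seeing the data and cite the protocol either way.

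**Working it through.** **Step 1: the texts side by side.**

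| Question | 5.6 | 11.4 | 2.1 |
|---|---|---|---|
| Whose QOL data count? | Not those of patients noncompliant with recommended treatment | All QOL data | No restriction |
| Does collection continue after serious noncompliance? | No | Not addressed | Assessment due at 6 and 12 months |
| Are earlier answers kept? | Not stated | Not stated | Not addressed |

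**Step 2: is the trigger defined?** Sections 6.1.6 and 6.1.7 define noncompliance and serious noncompliance by reference to regulations, institutional policy, IRB determinations, and harm or risk to participants. They do not deal with missed treatment. Section 5.6 gives no number of missed fractions, does not say which treatment component counts, and names no decision-maker. Section 5.1 protects changes that the oncologist finds necessary but does not address refusal by the patient.

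**Step 3: is a link to symptoms plausible?** Section 1.1 says treatment toxicity may hinder receipt of surgery. Section 1.3 reports grade 2 to 3 dysphagia in 43.6%, esophagitis in 46.8%, fatigue in 43.6% and nausea in 33.9% of patients in an earlier proton series. The link to noncompliance is a reasonable inference, but the protocol does not state it.

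**Step 4: illustrative size.** There is no figure of the plan to reproduce. Section 11.1 sets 20 + 20 = 40 patients on feasibility and says power calculations are not possible. The share lost and the score difference below are assumptions.

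Let N be the planned number, k the number lost, and d how much worse they score, in SD units. With adherent mean A, the mean of everyone is (1 − k/N)·A + (k/N)·(A − d) = A − (k/N)·d. The adherent mean is therefore too favourable by (k/N)·d. The 95% confidence half-width with n = N − k patients is t(0.975, n − 1)/√n, in SD units.

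| N | k | Share lost | Shift, d = 0.5 | Shift, d = 1.0 | Half-width at n = N − k |
|---|---|---|---|---|---|
| 40 | 0 | 0% | 0 | 0 | 0.320 |
| 40 | 2 | 5% | 0.025 | 0.05 | 0.329 |
| 40 | 4 | 10% | 0.05 | 0.10 | 0.338 |
| 40 | 8 | 20% | 0.10 | 0.20 | 0.361 |
| 20 (one setting) | 0 | 0% | 0 | 0 | 0.468 |
| 20 (one setting) | 4 | 20% | 0.10 | 0.20 | 0.533 |

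With N = 40 the shift runs from 0.025/0.329 = 8% to 0.20/0.361 = 55% of the half-width. It is below the half-width in every case shown.

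**The case against.** The strongest reply is that 5.6 is a stop list under a heading on duration of therapy, and that the analysis section speaks of all QOL data. A reader might infer that the plan prescribes an adherers-only analysis; the documents do not say so. That part of the reply stands, and it is why the point is conditional on the clause being applied. It does not dispose of the matter: a pure stop rule has no need to call data unusable, and 11.4 does not say which section prevails.

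The item is also headed serious noncompliance, and the parenthesis could be read as a threshold: noncompliance bad enough to make the answers uninterpretable. That is a fair reading. Without a definition it remains one of several.

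A reader might picture a patient who keeps attending interviews and whose answers are thrown away. That does not fit 5.6, because the same item ends QOL assessments. For months 6 and 12 the main loss is therefore data never collected, and removing the label alone would not restore them.

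Much poor tolerance is also handled elsewhere. Separate items cover "Adverse event(s) that, in the judgment of the investigator, may cause severe or permanent harm or which rule out continuation of study drug" and "General or specific changes in the patient's condition render the patient unacceptable for further treatment in the judgment of the investigator", and neither carries the label. The opening paragraph of 5.6 covers patients who no longer wish to continue therapy and says nothing about their data. This limits how many patients the noncompliance item would reach. It does not reduce the number to none, since both quoted items depend on the investigator's judgment and a patient who skips treatment because of symptoms could be classed as noncompliant.

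Finally, a reader might infer that the result would flatter protons against photons. Section 11.4 plans no such comparison for patient-reported outcomes, and Section 1.4 says such outcomes have not been reported for esophageal cancer.

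**Conclusion.** The point holds in a limited form. Section 5.6 ties both the collection and the usability of primary-endpoint data to compliance after baseline, while 2.1 and 11.4 contain no such limit. If the clause is applied, the 6- and 12-month results are conditional on adherence and would probably be somewhat too favourable.

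The illustrated shift is 0.025 to 0.20 SD. It rests wholly on two assumptions, a 5% to 20% share lost and scores 0.5 to 1.0 SD worse, and it is smaller than the sampling uncertainty of about 0.32 SD at 40 patients. It should not be expressed as a share of a detectable change: the plan sets no power target, and a shift in score-SD units is not on the same scale as a change-SD unit without further assumptions.

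Unlike sampling error, the shift would not shrink with more patients, and Section 11.1 intends these data as a basis for later studies. This is a cheap improvement rather than a serious flaw.

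**What to change.** - **Section 5.6:** delete the phrase declaring QOL data unusable. State that noncompliance with treatment does not by itself end QOL assessments in patients who still consent to them. Both changes are needed, since the first alone leaves later answers uncollected.
- **Section 11.4:** state that all patient-reported data from patients who started proton therapy are analysed regardless of compliance with proton therapy, chemotherapy or surgery. Report noncompliance with its reasons. Show a compliant-only analysis as a sensitivity analysis only.

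No change to any rule for stopping treatment is proposed.

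The cost is wording in two sections, one sensitivity table, and some further interviews on the existing schedule, which Section 5.4 already allows by phone. The means would describe proton therapy as actually received and may look slightly less favourable. The change does not address answers lost through the other items in the 5.6 list, such as progression or adverse events.

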6.0 REGULATORY AND REPORTING REQUIREMENTS

The entities providing oversight of safety and compliance with the protocol require reporting as outline below.

Protocol Version: 05/16/2023 Page 19 of 45

The Washington University Human Research Protection Office (HRPO) requires that all events meeting the definition of unanticipated problem or serious noncompliance be reported as outlined in Section 6.2.

6.1 **Definitions**

6.1.1 Adverse Events (AEs)

Definition: any unfavorable medical occurrence in a human subject including any abnormal sign, symptom, or disease.

Grading: the descriptions and grading scales found in the revised NCI Common Terminology Criteria for Adverse Events (CTCAE) version 4.03 will be utilized for all toxicity reporting. A copy of the CTCAE version 4.03 can be downloaded from the CTEP website.

Attribution (relatedness), Expectedness, and Seriousness: the definitions for the terms listed that should be used are those provided by the Department of Health and Human Services' Office for Human Research Protections (OHRP). A copy of this guidance can be found on OHRP's website: http://www.hhs.gov/ohrp/policy/advevntguid.html

6.1.2 Serious Adverse Event (SAE)

Definition: any adverse drug experience occurring at any dose that results in any of the following outcomes:

- o Death
- o A life-threatening adverse drug experience
- o Inpatient hospitalization or prolongation of existing hospitalization
- A persistent or significant disability/incapacity (i.e., a substantial disruption of a person's ability to conduct normal life functions)
- o A congenital anomaly/birth defect
- Any other experience which, based upon appropriate medical judgment, may jeopardize the subject and may require medical or surgical intervention to prevent one of the outcomes listed above

6.1.3 Unexpected Adverse Experience

Definition: any adverse drug experience, the specificity or severity of which is not consistent with the current investigator brochure (or risk information, if an IB is not required or available).

6.1.4 Life-Threatening Adverse Experience

Protocol Version: 05/16/2023 Page 20 of 45

Definition: any adverse drug experience that places the subject (in the view of the investigator) at immediate risk of death from the reaction as it occurred, i.e., it does not include a reaction that, had it occurred in a more severe form, might have caused death.

6.1.5 Unanticipated Problems

Definition:

- unexpected (in terms of nature, severity, or frequency) given (a) the research procedures that are described in the protocol-related documents, such as the IRB-approved research protocol and informed consent document; and (b) the characteristics of the subject population being studied;
- related or possibly related to participation in the research ("possibly related"
 means there is a reasonable possibility that the incident, experience, or
 outcome may have been caused by the procedures involved in the research);
 and
- suggests that the research places subjects or others at a greater risk of harm (including physical, psychological, economic, or social harm) than was previously known or recognized.

6.1.6 Noncompliance

Definition: failure to follow any applicable regulation or institutional policies that govern human subjects research or failure to follow the determinations of the IRB. Noncompliance may occur due to lack of knowledge or due to deliberate choice to ignore regulations, institutional policies, or determinations of the IRB.

6.1.7 Serious Noncompliance

Definition: noncompliance that materially increases risks, that results in substantial harm to subjects or others, or that materially compromises the rights or welfare of participants.

6.1.8 Protocol Exceptions

Definition: A planned deviation from the approved protocol that are under the research team's control. Exceptions apply only to a single participant or a singular situation.

Pre-approval of all protocol exceptions must be obtained prior to the event.

6.2 Reporting to the Human Research Protection Office (HRPO) at Washington University

The PI is required to promptly notify the IRB of the following events:

Protocol Version: 05/16/2023 Page 21 of 45

- Any unanticipated problems involving risks to participants or others which occur
 at WU, any BJH or SLCH institution, or that impacts participants or the conduct of
 the study.
- Noncompliance with federal regulations or the requirements or determinations of the IRB.
- Receipt of new information that may impact the willingness of participants to participate or continue participation in the research study.

These events must be reported to the IRB within 10 working days of the occurrence of the event or notification to the PI of the event. The death of a research participant that qualifies as a reportable event should be reported within 1 working day of the occurrence of the event or notification to the PI of the event.

6.3 Reporting to the Quality Assurance and Safety Monitoring Committee (QASMC) at Washington University

The PI is required to notify the QASMC of any unanticipated problem occurring at WU or any BJH or SLCH institution that has been reported to and acknowledged by HRPO as reportable. (Unanticipated problems reported to HRPO and withdrawn during the review process need not be reported to QASMC.)

QASMC must be notified within **10 days** of receipt of IRB acknowledgment via email to a QASMC auditor.

6.4 Timeframe for Reporting Required Events

Only AE's grade 3 or greater which are at least possibly related to the proton beam radiation therapy and listed in Appendix D, will be tracked Grade 3 or higher AE's possibly related to PBRT and found in Appendix D will be documented in clinical notes and the relatedness will be assessed in a timely fashion for the first year. After 12 months, the AE's will be reviewed at the 5 year follow-up time point through chart review and they will be assessed at that time. Please review Appendix D for a list of reportable adverse events. SAEs will be reported for 30 days after the end of concurrent chemoradiation regardless of the attribution. Thereafter, SAEs, which are possibly, probably, or definitely related will be reported for up to one year after the end of concurrent chemoradiation.

Protocol Version: 05/16/2023 Page 22 of 45

8.0 DATA SUBMISSION SCHEDULE

Case report forms with appropriate source documentation will be completed according to the schedule listed in this section.

Case Report Form	Submission Schedule
Original Consent Form	Prior to registration
On-Study Form	Prior to starting treatment
Chemotherapy Form Radiation Form	End of CRT
	Baseline
EQ-5D*	End of CRT
MDASI-plus*	8 weeks after end of CRT
SF-12*	4 months after end of CRT
MOS Social Support Survey*	6 months after end of CRT
4 item CES-D*	9 months after end of CRT
	12 months after end of CRT
	Baseline
Adverse Events Form**	At each on-treatment RT visit
Adverse Events Form	End of CRT
	Every 3-4 months during Year 1
Post-Op Form	4-6 weeks post-op
Follow Up Form	Every 3-4 months during Years 1-2
	Every 6 months during Years 3-5

^{*} The QOL forms will be entered via a computer-assisted interview program and will be stored on the computer's hard drive. The data will then be transferred via encrypted email, Dropbox, or encrypted flash drive and dumped into a password-protected database for data accumulation and merging. The other forms will be entered directly into the study REDCap database.

9.0 MEASUREMENT OF EFFECT

9.1 Toxicity

Toxicities related to radiation therapy, both acute (< 90 days from RT start) and late (> 90 days from RT start) will be documented and graded according to the NCI CTCAE v 4.0

9.2 Progression-Free Survival

PFS is defined as the duration of time from start of treatment to time of progression or death, whichever occurs first.

Protocol Version: 05/16/2023 Page 24 of 45

^{**} MD-reported AE's will be obtained from clinical note and chart review.

10.0 DATA AND SAFETY MONITORING

In compliance with the Washington University Institutional Data and Safety Monitoring Plan, the Principal Investigator will provide a Data and Safety Monitoring (DSM) report to the Washington University Quality Assurance and Safety Monitoring Committee (QASMC) semi-annually beginning six months after accrual has opened (if at least five patients have been enrolled) or one year after accrual has opened (if fewer than five patients have been enrolled at the six-month mark).

The Principal Investigator will review all patient data at least every six months, and provide a semi-annual report to the QASMC. This report will include:

- HRPO protocol number, protocol title, Principal Investigator name, data coordinator name, regulatory coordinator name, and statistician
- Date of initial HRPO approval, date of most recent consent HRPO approval/revision, date of HRPO expiration, date of most recent QA audit, study status, and phase of study
- History of study including summary of substantive amendments; summary of accrual suspensions including start/stop dates and reason; and summary of protocol exceptions, error, or breach of confidentiality including start/stop dates and reason
- Study-wide target accrual and study-wide actual accrual
- Protocol activation date
- Average rate of accrual observed in year 1, year 2, and subsequent years
- Expected accrual end date and accrual by cohort
- Objectives of protocol with supporting data and list the number of participants who have met each objective
- Early stopping rules with supporting data and list the number of participants who have met the early stopping rules
- Summary of toxicities separated by cohorts
- Abstract submissions/publications
- Summary of any recent literature that may affect the safety or ethics of the study

The study principal investigator and Research Patient Coordinator will monitor for serious toxicities on an ongoing basis. Once the principal investigator or Research Patient Coordinator becomes aware of an adverse event, the AE will be reported to the HRPO and QASMC according to institutional guidelines.

